15.1.3. Serious Adverse Events

Serious adverse events (SAEs) are those events recorded as ‘Yes’ in response to the “Does the Adverse Event meet seriousness criteria?” question on the Adverse Event/ Serious Adverse Event (AE/SAE) page of the eCRF.

A listing of SAEs (including deaths reported as SAEs) will be created.

15.1.4. Adverse Events Leading to Death

TEAEs leading to death are those events which have a ‘Most Extreme Grade’ recorded as ‘Grade 5 - Death related to AE’, or Seriousness Criteria has ‘Death’ ticked. Any AE leading to death will be also listed in a separate data listing from SAEs.

15.2. Deaths

If any patients die during the study as recorded on the *Death* page of the eCRF, the information will be presented in a data listing.

15.3. Laboratory Evaluations

Results from local laboratory data will be included in the reporting of this study for Hematology, Chemistry, and Cytokines. All laboratory parameters assessed for safety purposes will be evaluated locally. A list of laboratory assessments to be included in the outputs is included in Table 7-3 of the Protocol, Section 7.3.4. The treatment periods to be used for reporting laboratory data are defined in [Section 15](#).

Presentations will use SI Units (International System of Units).

Quantitative laboratory measurements reported as “< X”, i.e. below the lower limit of quantification (BLQ), or “> X”, i.e. above the upper limit of quantification (ULQ), will be converted to X for the purpose of quantitative summaries, but will be presented as recorded, i.e. as “< X” or “> X” in the listings.

Handling of retests and unscheduled measurements for laboratory results is included in [Section 6.3](#).

Hematology laboratory values will be summarized in a table. These summaries will be repeated for biochemistry (chemistry and cytokines). Furthermore, a listing of all laboratory data with values flagged as clinically significant will be presented with their corresponding NCI CTCAE grades and the classifications relative to the laboratory normal ranges will be presented for both hematology and biochemistry laboratory tests.

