#### 8.4.3 Reporting of Out-of-range Laboratory Test Results as Adverse Events

Out-of-range laboratory test results should be reported as AEs (not as abnormal laboratory values, ie, report as anemia, not low hemoglobin) if, in the opinion of the principal investigator, they are clinically significant. Abnormal laboratory results that are not considered to be clinically significant will not be reported as AEs. Significance of abnormal laboratory results should be documented in the study records.

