#### **9.6.1.2 Laboratory Abnormalities**

For laboratory tests covered by the NCI CTCAE version 4.03 the study team will grade laboratory data accordingly. For laboratory tests covered by NCI CTCAE, a grade 0 will be assigned for all non-missing values not graded as 1 or higher. For laboratory tests where grades are not defined by NCI CTCAE, results will be graded by the low/normal/high classifications based on laboratory normal ranges.

The following by-treatment summaries will be generated separately for hematology, biochemistry, and other laboratory:

- Frequency table for newly occurring on-treatment grades 3 or 4 and all grades
- Shift tables of laboratory and ECG data using NCI CTCAE grades to compare Baseline to the worst on-treatment value
- Listing of all clinically relevant laboratory data and relevant ECG data with values flagged to show the corresponding NCI CTCAE grades and the classifications relative to the laboratory normal ranges

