3.3. Changes to Analysis from Protocol

The following are documented changes to analysis from protocol:

- Tables/Listings for change from baseline and shift tables are removed from the analysis for vital signs and ECG data. Note that vital signs will only be collected at baseline.

4. Planned Analyses

A final analysis after database lock is planned for this study.

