15.3.3. NCI CTCAE Grading for Laboratory Data

Laboratory measurements will be graded by the study team using NCI CTCAE version 4.03 as defined by National Cancer Institute.

Laboratory tests covered by NCI CTCAE are as follows (found under 'Investigations' in the link above unless otherwise specified):

Hematology:

- Hemoglobin
- White blood cell count (Leukocytes)
- Platelet count
- Absolute neutrophils count
- Absolute lymphocyte count

Biochemistry:

- Creatinine
- Sodium (see hypernatremia/hyponatremia)
- Potassium (see hyperkalemia/hypokalemia)
- Albumin (see hypoalbuminemia)
- Total bilirubin (and direct/indirect)
- Alkaline phosphatase
- ALT
- AST
- Magnesium (see hypermagnesemia/ hypomagnesemia)
- Corrected Calcium (see hypercalcemia/hypocalcemia) – see [Section 15.3.1](#)
- Glucose (see hyperglycemia/hypoglycemia)
- Amylase
- Inorganic phosphate (see hypophosphatemia)
- Lipase

For laboratory tests covered by NCI CTCAE, a grade 0 will be assigned for all non-missing values not graded as 1 or higher. Any missing laboratory value will consequently have a missing CTCAE Grade.

If CTCAE Grade 1, specified in the NCI CTCAE version 4.03 documentation, requires LLN/ULN follow the rules below.

For LLN:

- If LLN is above or equal to the lower value of the range for the Grade 1, then continue with the process as specified in the documentation.
- If LLN is below the lower value of the range for the Grade 1 then check if the laboratory test value is equal to the lower value, if yes set this to Grade 1. If the laboratory test value is above the lower value of the range for the Grade 1, then set to Grade 0. Else grade as per the rules for Grade 2 onwards.

For ULN:

- If ULN is below or equal to the higher value of the range for the Grade 1, then continue with the process as specified in the documentation.
- If ULN is above the higher value of the range for the Grade 1 then check if the laboratory test value is equal to the higher value, if yes set this to Grade 1. If the laboratory test value is below the higher value of the range for the Grade 1, then set to Grade 0. Else grade as per the rules for Grade 2 onwards.

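### The SAP text specifies no patient count of laboratory abnormalities by CTCAE grade, although the protocol requires one, and does not declare the change

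*SAP*

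**What the plan says.** Protocol 9.6.1.2 lists three laboratory outputs, to be produced separately for hematology, biochemistry and other laboratory tests:

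1. "Frequency table for newly occurring on-treatment grades 3 or 4 and all grades"
2. "Shift tables of laboratory and ECG data using NCI CTCAE grades to compare Baseline to the worst on-treatment value"
3. A listing of clinically relevant results, flagged with CTCAE grade and position relative to the normal range.

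SAP 15.3 is shorter. It states "Hematology laboratory values will be summarized in a table", repeats the summary for biochemistry (chemistry and cytokines), and then provides "a listing of all laboratory data with values flagged as clinically significant will be presented with their corresponding NCI CTCAE grades". SAP 15.3.3 sets out in detail how results are graded, including that "a grade 0 will be assigned for all non-missing values not graded as 1 or higher".

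The section that records departures from the protocol, SAP 3.3, has one entry: "Tables/Listings for change from baseline and shift tables are removed from the analysis for vital signs and ECG data". It does not mention laboratory data.

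SAP 6.2 confines the rollover baseline to describing patients and their disease at entry. It rules out change-from-baseline analysis because patients were already taking IMCgp100 in the parent study.

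**The concern.** Two of the protocol's three laboratory outputs are not in the SAP text, and the list of changes does not say that they were removed. The second protocol output covers laboratory and ECG data together. SAP 3.3 removes the ECG half by name, so a reader would reasonably conclude that the laboratory half stands.

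The grade frequency table matters more. The AE tables count patients with grade 3 or higher events, but a laboratory result reaches those tables only if it is reported as an AE. Protocol 8.4.3 says "Abnormal laboratory results that are not considered to be clinically significant will not be reported as AEs". The grade frequency table is the one output that counts severe results without depending on that judgement. The primary endpoint of this study is AE incidence and a secondary objective is long-term safety, so this count is a natural complement to the AE tables.

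**Working it through.** No formula applies. The study is descriptive, with no sample size calculation (Protocol 9.9) and no hypothesis test (SAP 6.5), and the plan states no figure to reproduce. The check sets the required outputs beside the specified ones.

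| Protocol 9.6.1.2 output | In SAP 15.3 to 15.3.3? | Removal declared in SAP 3.3? |
|---|---|---|
| Frequency table, newly occurring grade 3 or 4 and all grades | No | No |
| Shift tables, baseline to worst on-treatment grade | No | ECG only, not laboratory |
| Listing with grades | Yes | Not needed |

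**How many parameters are graded.** SAP 15.3.3 lists 5 hematology tests and 14 biochemistry tests (bilirubin counted once): 5 + 14 = 19. Each non-missing result receives a grade of 0 or higher. The only laboratory output to which SAP 15.3 attaches these grades is the listing.

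**Whether SAP 6.2 explains the gap.** There are three elements to consider.

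- Shift tables compare with baseline, so the limit on the rollover baseline is a sufficient reason to omit them.
- Newly occurring, on its natural reading, needs a reference grade. The same limit can explain leaving that element out.
- A count of patients by worst on-treatment grade needs no reference value. SAP 6.2 gives no reason for having no count by grade at all.

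**Whether another table supplies the count.** SAP 15.1.1.1 tabulates patients with TEAEs of any grade and of grade 3 or higher. Under Protocol 8.1.1, an abnormal result is an AE if it causes signs or symptoms, is clinically significant, needs therapy, or needs a change in study medication. Results that meet any of these criteria enter the TEAE tables. A grade 3 or 4 result that meets none of them does not.

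**Whether the value summary supplies it.** Appendix 1 of the SAP sets the univariate statistics as n, mean, standard deviation, median, minimum and maximum. The minimum and maximum show that an extreme value occurred, but not how many patients reached grade 3 or 4. If the summary is by visit, SAP 6.3 also excludes unscheduled measurements from it.

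The remaining set is therefore grade 3 or 4 results that meet no AE criterion. The SAP text places them in a listing and in no patient count.

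**The case against.** The strongest reply concerns the shells. SAP section 8 leaves the format and content of tables to template shells, which were not among the documents. SAP 15.3 does not exclude grade rows from its table. The grade 0 rule, the best/worst-case rule in SAP 6.3 and the application of the Section 15 treatment periods to laboratory data would all suit a worst-grade table. A reader might infer that the SAP has definitely dropped the count. The documents do not support that. They show only that the SAP text does not specify it and does not declare its removal.

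Three other strong inferences also fail.

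- A reader might infer that SAP 6.2 is irrelevant because a worst-grade count needs no baseline. The protocol's table is of newly occurring grades, so SAP 6.2 does bear on it. The baseline-free count is a substitute for that table.
- A reader might infer that severe toxicity would be judged from means alone. The summaries include the minimum and maximum, and the listing shows individual grades.
- A reader might infer from Protocol 8.4.3 alone that every result not called clinically significant escapes the AE tables. Protocol 8.1.1 brings in those that cause symptoms, need therapy or change study medication.

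Multiplying 19 parameters by weekly draws would measure the volume of testing. It would not estimate the number of severe results left uncounted, and the documents give no basis for such an estimate.

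These objections narrow the point but do not remove it. The general statement in SAP 6.2 is not an entry in SAP 3.3, and neither section mentions the frequency table.

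**Conclusion.** The point holds in a limited form. The SAP text conflicts with Protocol 9.6.1.2 on two laboratory outputs and declares neither change. Followed as written, it gives no patient count by grade for any of the 19 graded parameters. Grade 3 or 4 results outside the AE criteria would be visible only line by line.

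This rests on two assumptions: that the shells do not contain a grade count, and that the listing in SAP 15.3 covers all laboratory results with their grades. If the shells do contain the table, what remains is a documentation fault, since SAP 15.3 and 3.3 should still say what was kept and what was removed.

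The number of patients affected cannot be derived from the documents. The consequence is confined to descriptive safety reporting; the primary variable and all other results are unchanged.

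**What to change.** **SAP 15.3.** Add a table of the number and percentage of safety-set patients by worst on-treatment CTCAE grade, showing all grades and grade 3 or 4, for each graded parameter. Use scheduled, unscheduled and retest values, in line with the worst-case rule in SAP 6.3, and the on-treatment period in SAP Section 15. Tests that SAP 15.3.3 grades in both directions (sodium, potassium, magnesium, corrected calcium, glucose) need separate rows for high and low.

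**Newly occurring.** Either define the reference grade, or state that the worst on-treatment grade replaces this element.

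**SAP 3.3.** Record that change, and record the removal of the laboratory shift tables with the reason already given in SAP 6.2.

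If the shells already include the table, only the wording in 15.3 and 3.3 needs to change.

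The cost is one extra descriptive table, built from grades that are already derived, and a short entry in SAP 3.3. The drawback is that some counted abnormalities may predate rollover entry, since a worst-grade count does not separate new from continuing abnormalities. A footnote should say so.

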15.3.1. Laboratory Specific Derivations

The following laboratory parameters will be derived as follows:

- Corrected Calcium [mmol/L]* = (0.02 * (Normal Albumin [g/L] – Serum Albumin [g/L])) + Serum Calcium [mmol/L]
 - * This correction will only be applied for records at the patient/visit level where albumin is less than the lower limit of normal. For records where albumin is greater than or equal to the lower limit of normal, no correction will be applied,

and the Corrected Calcium value will equal the calcium (uncorrected) value, as collected on the eCRF.

- Normal albumin is assumed to be 40 g/L.
- Note: The reference ranges for Corrected Calcium will be derived on a patient by patient, visit by visit level, as the same reference ranges collected locally for calcium (uncorrected), which is a parameter collected directly from eCRF.

All other laboratory parameters are available from the data collected on the eCRF. Local laboratory results will be converted into SI units (International System of Units) and presentations will use SI Units.

15.3.2. Laboratory Reference Ranges and Markedly Abnormal Criteria

The following laboratory tests do not have grades defined by NCI CTCAE:

Hematology:

[figure not shown]
- Hematocrit
- Absolute basophils
- Absolute eosinophils
- Absolute monocytes

Biochemistry:

- Bicarbonate
- Calcium (uncorrected) – as collected directly from eCRF
- Chloride
- Blood urea nitrogen
- Urea
- Gamma-interferon
- Interleukin-6
- Interleukin-10
- Tumor necrosis factor- α

For these laboratory tests, results will be graded by the low/normal/high classifications based on laboratory normal ranges. In this case, quantitative laboratory measurements will be compared with the relevant laboratory reference ranges in SI units and categorized as:

- Low: Below the lower limit of the laboratory reference range.
- Normal: Within the laboratory reference range (upper and lower limit included).
- High: Above the upper limit of the laboratory reference range.

The lower and upper limit will be referred to in outputs as LLN = Lower Limit Normal and ULN = Upper Limit Normal, respectively.

15.3.3. NCI CTCAE Grading for Laboratory Data

Laboratory measurements will be graded by the study team using NCI CTCAE version 4.03 as defined by National Cancer Institute.

Laboratory tests covered by NCI CTCAE are as follows (found under 'Investigations' in the link above unless otherwise specified):

Hematology:

- Hemoglobin
- White blood cell count (Leukocytes)
- Platelet count
- Absolute neutrophils count
- Absolute lymphocyte count

Biochemistry:

- Creatinine
- Sodium (see hypernatremia/hyponatremia)
- Potassium (see hyperkalemia/hypokalemia)
- Albumin (see hypoalbuminemia)
- Total bilirubin (and direct/indirect)
- Alkaline phosphatase
- ALT
- AST
- Magnesium (see hypermagnesemia/ hypomagnesemia)
- Corrected Calcium (see hypercalcemia/hypocalcemia) – see [Section 15.3.1](#)
- Glucose (see hyperglycemia/hypoglycemia)
- Amylase
- Inorganic phosphate (see hypophosphatemia)
- Lipase

For laboratory tests covered by NCI CTCAE, a grade 0 will be assigned for all non-missing values not graded as 1 or higher. Any missing laboratory value will consequently have a missing CTCAE Grade.

If CTCAE Grade 1, specified in the NCI CTCAE version 4.03 documentation, requires LLN/ULN follow the rules below.

For LLN:

- If LLN is above or equal to the lower value of the range for the Grade 1, then continue with the process as specified in the documentation.
- If LLN is below the lower value of the range for the Grade 1 then check if the laboratory test value is equal to the lower value, if yes set this to Grade 1. If the laboratory test value is above the lower value of the range for the Grade 1, then set to Grade 0. Else grade as per the rules for Grade 2 onwards.

For ULN:

- If ULN is below or equal to the higher value of the range for the Grade 1, then continue with the process as specified in the documentation.
- If ULN is above the higher value of the range for the Grade 1 then check if the laboratory test value is equal to the higher value, if yes set this to Grade 1. If the laboratory test value is below the higher value of the range for the Grade 1, then set to Grade 0. Else grade as per the rules for Grade 2 onwards.

15.4. ECG Evaluations

Results from the ECG (Electrocardiogram) as recorded by the Investigator on the eCRF at Screening and at End of Treatment will be included in the reporting of this study. The treatment periods to be used for reporting ECG data are defined in [Section 15](#). No change from baseline values for ECG will be reported for this study.

The following ECG parameters will be reported for this study:

- PR Interval (msec)
- QRS Interval (msec)
- QT Interval (msec)
- QTcB Interval (msec)
- QTcF Interval (msec)
- Overall assessment of ECG (Investigator's judgment):
 - Normal
 - Abnormal, Not Clinically Significant (ANCS)
 - Abnormal, Clinically Significant (ACS)

The observed ECG values will be shown through a listing. Values meeting markedly abnormal criteria will be flagged in the listing.

15.4.1. ECG Specific Derivations

No extra ECG derivations are necessary, as all parameters are collected from eCRF page.

15.4.2. ECG Markedly Abnormal Criteria

Markedly abnormal quantitative ECG measurements will be identified in accordance with the following predefined criteria for varying degrees of abnormality for prolonged QTc (based on ICH – E14 standard ranges)

- Absolute values for QTcB interval and QTcF will be classified as:
 - Missing result
 - ≤450 msec (i.e. 'Normal')
 - >450-480 msec
 - >480-500 msec
 - >500 msec

15.5. Vital Signs

The treatment periods will not be used for reporting vital signs data, as defined in [Section 15](#). Vital signs, excluding weight, are only recorded up to and at baseline. Weight is collected throughout the study period. The following Vital Signs measurements will be reported for this study:

- Systolic Blood Pressure (mmHg)
- Diastolic Blood Pressure (mmHg)
- Respiratory Rate (breaths/min)
- Pulse Rate (bpm)
- Temperature (°C)
- Weight (kg)

All measurements apart from weight are taken in a sitting position after at least 5 minutes of rest.

All vital sign evaluations performed will be listed with their classifications relative to the vital signs markedly abnormal criteria given in [Section 15.5.2](#) below.

15.5.1. Vital Signs Specific Derivations

Weight can be entered on the eCRF in kg or lbs. Any weight assessments entered in lbs will be converted to kg by dividing by 2.205.

15.5.2. Vital Signs Markedly Abnormal Criteria

Markedly abnormal quantitative Vital Signs measurements observed values will be identified in accordance with the following predefined markedly abnormal criteria:

Variable	Unit	Low	High
SBP	mmHg	≤ 90 mmHg	Grade 1: 120 to 139 mmHg Grade 2: 140 to 159 mmHg Grade 3: ≥ 160 mmHg
DBP	mmHg	≤ 60 mmHg	Grade 1: 80 to 89 mmHg Grade 2: 90 to 99 mmHg Grade 3: ≥ 100 mmHg
Respiratory Rate	breaths/ min	< 10 breaths/min	≥ 20 breaths/min
Heart rate	bpm	≤ 60 bpm	≥ 100 bpm
Body temperature	°C	NA	Grade 1: 38.0 – 39.0 °C Grade 2: >39.0 – 40.0 °C Grade 3/4: >40.0 °C
Weight	kg	NA	NA

Since weight has no Low or High markedly abnormal criteria in this rollover study, it will have “NA” in lieu of “Low”, “Normal” or “High” in listings. For other vital sign, a value that is not Low nor High will be represented as “Normal”.

15.6. Physical Examination

Physical Examination results will be listed, and abnormalities will be flagged.

16. Exploratory Objectives

16.1. Immunogenicity

Data pertaining to the Immunogenicity exploratory endpoints will be listed and will be based on the SAF analysis set.

17. Other Data Not Summarized or Presented

The CRF pages

not summarized or presented are:

- Principal Investigator Signatures
- Subsequent Cycle Status
- Safety Follow-up D90

18. References

- ICH Steering Committee. (2005). *ICH Harmonised Tripartite Guideline: The clinical evaluation of QT/QTc Interval Prolongation and Proarrhythmic Potential for Non-Antiarrhythmic Drugs E14*. Retrieved from http://www.ich.org/fileadmin/Public_Web_Site/ICH_Products/Guidelines/Efficacy/E14/E14_Guideline.pdf
- Parent X, S. C. (2009). ["Corrected" calcium: calcium status underestimation in non-hypoalbuminemic patients and in hypercalcemic patients]. *PubMed*, 1. doi:10.1684/abc.2009.0348
- Services, U. D. (2010, June 14). *National Institute of Health*. Retrieved April 2, 2019, from CTCAE: https://evs.nci.nih.gov/ftp1/CTCAE/CTCAE_4.03/CTCAE_4.03_2010-06-14_QuickReference_5x7.pdf

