### 4.4 Secondary Endpoints

- Tolerability: Dose interruptions, reductions, and dose intensity of IMCgp100
- Assessments of anti-IMCgp100 antibody formation
- Date of death in all patients treated with IMCgp100

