**Table 4-1 Objectives and Related Endpoints**

Objective(s)	Endpoint(s)
Primary	
To determine the number of patients with adverse events associated with IMCgp100 treatment	Incidence of adverse events
Secondary	
To characterize the long-term safety (> 1 year dosing) and tolerability of IMCgp100	Tolerability: Dose interruptions, reductions, and dose intensity of IMCgp100

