**Table 7-1 Schedule of Study Assessments**

Procedure	Protocol Section	Screening Phase	Treatment Phase						Follow-up Phase			
			Rollover Cycle 1		Rollover Cycle 2		End of Treatment	90-day Safety Follow Up	Survival Follow Up			
		Screening a	Day 1 a	Day 8	Day 15	Day 22	Day 1	Day 8	Day 15	Day 22		

irRECIST = immune-related Response Evaluation Criteria in Solid Tumors.
 
a. Screening and Rollover Cycle 1 Day 1 (RC1D1) may be the same day, no procedures or events need to be repeated.
 
b. At Screening (or RC1D1), prior to IMCgp100 infusion, a complete physical examination will be performed. From RC1D8 onwards, a short physical examination will be performed. See Section 7.3.1.
 
c. Frequent vital signs, as per institutional standard, should be implemented during any required inpatient observations at a minimum of every 4 hours. (Refer to Section 7.3.2 for additional details).
 
d. Hematology panel should be obtained at Screening, before every IMCgp100 dose, and at the End of Treatment visit as well.
 
e. Chemistry panel should be obtained at Screening, before every dose of IMCgp100, and at the End of Treatment visit.
 
f. Cytokine panel should be obtained in all patients with a suspected occurrence of cytokine release syndrome. See Section 7.3.4.
 
g. Pregnancy testing is required in all females of childbearing potential. At Screening, a serum pregnancy test must be performed within 72 hours before the first dose of IMCgp100. During the study (Day 1 of each cycle starting with Cycle 2) a serum or urine pregnancy test must be performed. At End of Treatment, a serum or urine pregnancy test must also be performed.
 
h. Please refer to Section 6.1 Study Treatment for details of weekly IMCgp100 administration.
 
i. Immunogenicity samples are to be taken at Day 1 of all odd-numbered cycles and at End of Treatment. All samples are to be collected immediately before IMCgp100 infusion.
 
j. Target and non-target tumors to be assessed for radiographic disease progression by modified irRECIST criteria (refer to Section 7.3.5). Disease assessment to be performed at a minimum of 12 week intervals.
												

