#### 9.6.1.4 Tolerability

Tolerability of study treatment will be assessed by summarizing the number of treatment dose interruptions and dose reductions. Reasons for dose interruptions and dose reductions will be listed by patient and summarized.

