2.2. Secondary Objectives

- To characterize the long-term safety (> 1 year dosing) and tolerability profile associated with treatment with IMCgp100
- To evaluate the incidence of anti-IMCgp100 antibody formation following multiple infusions of IMCgp100
- To estimate the overall survival (OS) in patients treated with IMCgp100.

3. Study Design

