6.2. Baseline

Unless otherwise specified, baseline is defined as the last non-missing measurement (including unscheduled assessments) taken prior to the first dose of rollover treatment received (i.e., Rollover Cycle 1 Day 1 RC1D1 pre-dose). In the case where the date of the last non-missing measurement and the first dose date of rollover treatment coincide, that measurement will be considered pre-dose and included in the baseline calculation as appropriate. This will be the rule for demography, other baseline characteristics (including disease status), laboratory data, and physical examination data. For ECGs and vital signs, where the time of assessment is recorded, if the last non-missing measurement and the reference start date coincide, then only if the time of the measurement is prior to the time of first dose will the measurement be considered pre-dose and included in the baseline calculation. Furthermore, because ECGs are supposed to be taken pre-dose on RC1D1, any RC1D1 measurements of ECGs with a time on or after the time of first dose will be queried with Data Management.

Note that baseline measurements made in the rollover study will only be used for summarizing baseline demographic information and disease characteristics. It will not be used for analyzing change from baseline, as comparisons to these baseline values cannot take into account the fact that patients were already taking IMCgp100 in their parent study.

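### The SAP drops the protocol's count of dose reductions without declaring it and, a lesser point, plans only a listing for the secondary objective of antibody incidence

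*SAP*

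**What the plan says.** **Dose reductions.** Protocol 4.4 and Table 4-1 define the secondary tolerability endpoint as "Tolerability: Dose interruptions, reductions, and dose intensity of IMCgp100". Protocol 9.6.1.4, under Secondary Analyses, gives the analysis: "Tolerability of study treatment will be assessed by summarizing the number of treatment dose interruptions and dose reductions", followed by "Reasons for dose interruptions and dose reductions will be listed by patient and summarized". SAP 13 keeps the interruptions half of this. It summarises how many interruptions occurred, lists their reasons and does not mention reductions. SAP 13.1 defines an interruption as a whole dosing visit missed and gives no definition of a reduction. Reduced doses appear there only in the cycle-counting notes, where they do not stop a cycle from counting as completed. SAP 3.3, where departures from the protocol are recorded, covers only vital signs and ECG.

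**Antibodies.** SAP 2.2 and Protocol 4.2 share a secondary objective: "To evaluate the incidence of anti-IMCgp100 antibody formation following multiple infusions of IMCgp100". The matching endpoint in Protocol 4.4 is "Assessments of anti-IMCgp100 antibody formation". Table 7-1 schedules the data: "Immunogenicity samples are to be taken at Day 1 of all odd-numbered cycles and at End of Treatment". The only SAP analysis text is section 16.1, under Exploratory Objectives: "Data pertaining to the Immunogenicity exploratory endpoints will be listed and will be based on the SAF analysis set".

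**The concern.** Followed as written, the SAP text leaves one named component of a secondary endpoint uncounted and one secondary objective without a proportion.

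The reductions gap matters more. The protocol made a specific promise, the SAP kept half of it, and the place for declaring changes is silent. The number of reductions also has meaning within the protocol: the text after Table 6-2 ties stopping treatment to how many a patient has had. Tolerability over long dosing is one of the main things a rollover study can describe, and a reader of the report would expect to see how many patients had their dose lowered and why.

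For antibodies, patients give repeated blood samples towards an objective worded as an incidence, and the planned output leaves the reader to do the counting.

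**Working it through.** The plan has no sample size, power or event figure to reproduce. The check is a comparison of text, plus one calculation to see whether another planned summary could replace the missing count.

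**Step 1. Protocol and SAP side by side.**

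| Item | Protocol | SAP text |
|---|---|---|
| Number of interruptions | Summarised (9.6.1.4) | Summarised (13) |
| Number of reductions | Summarised (9.6.1.4); named in 4.4 and Table 4-1 | No summary, no definition |
| Reasons for interruptions | Listed and summarised | Listed |
| Reasons for reductions | Listed and summarised | Not mentioned |
| Dose intensity | Summarised (9.4) | Summarised (13, 13.1) |
| Departure declared in SAP 3.3 | – | No |

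**Step 2. Can relative dose intensity (RDI) replace the count?** From SAP 13.1, with A = total actual dose, P = total planned dose and D = duration in days:

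- Dose intensity = (A/D) × 7
- Planned dose intensity = (P/D) × 7
- RDI = 100 × [(A/D) × 7] / [(P/D) × 7] = 100 × A/P, because D cancels.

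P is built from the parent-study dose, or from the dose set at entry if it was changed. A reduction during rollover therefore lowers A but not P, as do an omitted dose and a partly delivered one.

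Take 52 planned weekly doses of one unit, which is 52/4 = 13 cycles. These histories are assumptions for arithmetic only.

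- (a) Prescribed dose halved from dose 27 on: A = 26 + 26 × 0.5 = 39.
- (b) 13 doses omitted in mid-course: A = 52 − 13 = 39.
- (c) 26 infusions half delivered, prescription unchanged: A = 26 + 26 × 0.5 = 39.

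RDI = 39/52 = 75.0% in all three.

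The other exposure quantities described in SAP 13 and 13.1 separate (b) but not (a) from (c):

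- (a) and (c) each show 0 interruptions and 13 of 13 cycles completed, because a reduced dose still counts towards a completed cycle and a partial dose is not an interruption.
- (b) shows 1 interruption and 13 − 4 = 9 completed cycles if the omissions are consecutive, since 13 successive weekly doses touch 4 cycles.
- (b) shows up to 13 interruptions and 0 completed cycles if one dose is missed in each cycle.

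Only (a) contains a dose reduction.

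**Step 3. Antibodies.** Over one year (13 cycles), sampling falls on Day 1 of cycles 1, 3, 5, 7, 9, 11 and 13, which is 7 samples, plus End of Treatment, making 8. The data for a proportion are therefore scheduled. SAP 16.1 names the population (SAF) but plans no proportion and does not say how to treat a SAF patient with no evaluable sample.

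**Step 4. What can be estimated.** SAP 6.2 says comparisons with rollover baseline "cannot take into account the fact that patients were already taking IMCgp100 in their parent study". For the same reason, a positive rollover sample may reflect antibodies formed in the parent study. Rollover samples alone support a prevalence during rollover, not a new-onset incidence.

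**The case against.** **The shells may hold the tables.** SAP 8 says the shells fix the format and content of the outputs, and they were not supplied. This stands as a limit: a reader might infer that no output will separate a reduction from a partly delivered infusion, and that cannot be shown. Adverse-event data are listed as recorded, and the form has a field for action taken with study drug (SAP 15.1, 15.1.2), so some event-driven reductions may be visible there. A listing is still not the summary that Protocol 9.6.1.4 promises, and a shell does not replace a definition in the SAP.

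**The antibody listing does have a population.** A reader might infer that no denominator is set. SAP 16.1 names the SAF, and SAP 5.3 defines it. What is missing is the narrower rule for patients without an evaluable sample.

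**The exploratory label has a precedent.** A reader might take the label as proof that the SAP demoted the objective. Protocol 9.7 itself puts overall survival, also a secondary objective, and an immunogenicity item under exploratory analyses. The body of that immunogenicity item is redacted and cannot be judged. The label alone is weak evidence; the point rests on the missing proportion.

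**A listing is defensible in patients already exposed.** This has force, and it is why the antibody part carries less weight. The protocol endpoint is worded as assessments, which a listing does report. But the objective in SAP 2.2 is worded as an incidence, and if a listing is the deliberate choice, the SAP should say so.

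**The study is small in ambition and purely descriptive.** True: there is no formal sample size and no hypothesis testing. That makes counts easy to supply and does not remove a stated endpoint.

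**Conclusion.** The point holds in two parts of unequal weight.

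1. Dose reductions, firm: a component of the secondary tolerability endpoint has neither a definition nor a count in the SAP text. Reasons for interruptions are downgraded to a listing, reasons for reductions are absent, and SAP 3.3 declares none of it. Relative dose intensity cannot recover the count.
2. Antibodies, modest: a secondary objective worded as incidence has only a listing on the SAF, with no proportion and no rule for missing evaluable samples.

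No result can be said to change by a given amount. The documents give no patient numbers, and the 75.0% illustration rests on assumed dosing histories. It shows only that dose intensity is not a count of reductions. The conclusion covers the SAP text without the shells.

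A reader might also infer that the long-term safety objective (more than 1 year of dosing) obliges an adverse-event table split by time on treatment. The documents do not support that: neither promises one, and Table 4-1 maps the objective to tolerability. The primary adverse-event endpoint is not affected. The gaps should be closed before the final analysis, but they do not threaten the study's main result.

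**What to change.** **SAP 13 and 13.1.** Add to the tolerability summary the number of patients with a dose reduction, the number of reductions, and summarised reasons for interruptions and, where collected, for reductions. Define a reduction for analysis as a prescribed dose lower than the previous rollover dose. Count partly delivered infusions and dose changes made at entry separately.

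**SAP 16.1.** Add n/N (%) of patients antibody-positive at any rollover sample, and state how many SAF patients have no evaluable sample. Label it prevalence during rollover. Report treatment-emergent incidence only if parent-study samples from before the first IMCgp100 dose are available. An exact 95% confidence interval is optional.

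**SAP 3.3.** If either item is dropped on purpose, declare it there with the reason.

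**Cost.** A few rows in one table, one small antibody table and SAP wording. Protocol 6.1 already requires dose changes to be recorded, SAP 13.1 uses the actual dose at each visit, and Table 7-1 already schedules the antibody samples. The documents do not show whether the case report form has a reason field for reductions, or whether parent-study pre-dose antibody samples exist; both should be checked first.
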